### **8.1.1 Demographics**

Demographics and baseline characteristics will be summarized for all treated subjects by treatment arm for the Main Study and separately on the overall EP-RS population.

Demographics include age, weight, height, BMI, gender, race, and ethnicity. Baseline characteristics will be summarized as continuous variables (where appropriate) and as categorical variables, including HCV genotype subtype, most recent HCV treatment history, baseline HCV RNA level, and fibrosis stage.

Summary statistics (N, mean, median, SD, and range) will be generated by treatment arm for continuous variables (e.g., age and BMI), and the number and percentage of subjects will be presented for categorical variables (e.g., sex and race).

Study drug exposure and compliance will be summarized by treatment arm and separately on the overall EP-RS population. Treatment compliance to study drug will be calculated based on the percentage of tablets\*\*\* taken relative to the total tablets\*\*\* expected to be taken for each tablet\*\*\* type G/P, RBV, SOF tablets as applicable. A subject is considered to be compliant if the percentage is between 80% and 120% for each tablet type. Compliance will be calculated for each subject and summarized with the mean, median, standard deviation, minimum, and maximum. The percentage of compliant subjects will be summarized.

\*\*\*RBV Dosage Form to be determined by dispensing pharmacy.

## **8.1.2 Efficacy**

All efficacy analyses will be performed on the mITT and EP-RS populations, unless otherwise specified. Plasma HCV RNA levels will be determined for each sample collected by the central laboratory using the Roche COBAS® AmpliPrep/COBAS® TaqMan® HCV Quantitative Test, v2.0. The notation "HCV RNA < LLOQ" is used to represent all HCV RNA values < 15 IU/mL that are HCV RNA detected or HCV RNA not detected. HCV RNA  $\geq$  LLOQ are all quantifiable values.

### **8.1.2.1 Primary Efficacy Endpoints**

The primary efficacy endpoints for the mITT population are the difference in SVR12 (HCV RNA < LLOQ 12 weeks after the last actual dose of study drug) rates between Arm A and Arm B in non-cirrhotic subjects, and difference in SVR12 rates between Arm C and Arm D in cirrhotic subjects.

The difference in SVR12 rates will be summarized with a two-sided 95% confidence interval for the comparison between Arm A and Arm B in non-cirrhotic subjects, and for the comparison between Arm C and Arm D in cirrhotic subjects. The number and percentage of subject achieving SVR12 by treatment arm will also be summarized with a two-sided 95% confidence interval. The confidence interval for the difference in SVR12

rates will be calculated using Wilson's score method. The confidence interval for the SVR12 rates by treatment arm will be calculated using the normal approximation to the binomial distribution if the number of subjects who failed to achieve SVR12 is at least 5. If the number of subjects who failed to achieve SVR12 is less than 5, Wilson's score method will be used instead.

A summary of reasons for SVR12 non-response (e.g., on-treatment virologic failure, relapse, other) will be provided.

### **8.1.2.2 Secondary Efficacy Endpoints**

The secondary efficacy endpoints for the mITT population in the Main Study are:

- the difference in SVR12 rates between G/P given for 12 weeks (Arm A and C combined) and G/P given for 16 weeks (Arm B and D combined);
- the difference in the percentage of subjects with on-treatment virologic failure (confirmed increase of  $> 1 \log_{10}$  IU/mL above nadir during treatment, confirmed HCV RNA  $\geq 100$  IU/mL after HCV RNA  $<$  LLOQ during treatment, or HCV RNA  $\geq$  LLOQ at the end of treatment with at least 6 weeks of treatment) between Arm A and Arm B in non-cirrhotic subjects, and between Arm C and Arm D in cirrhotic subjects;
- the difference in the percentage of subjects with post-treatment relapse (defined as confirmed HCV RNA  $\geq$  LLOQ between end of treatment and 12 weeks after the last dose of study drug among subjects who completed treatment as planned with HCV RNA  $<$  LLOQ at the end of treatment, excluding subjects with reinfection) between Arm A and Arm B in non-cirrhotic subjects, and between Arm C and Arm D in cirrhotic subjects.

For the analysis of relapse, completion of treatment is defined as any subject with study drug duration of 77 days or greater for 12-week arms (Arms A and C), or 105 days or greater for 16-week arm (Arm B and D).

The difference in SVR12 rates between 12 week (Arms A+ C) and 16 week (Arms B+D)

---

treatment durations will be summarized calculated along with a two-sided 95% confidence interval using Wilson's score method. The difference in the percentage of subjects with on-treatment virologic failure and post-treatment relapse will be summarized with two-sided 95% Wilson score intervals, as will the percentage of subjects with on-treatment virologic failure and post-treatment relapse in each treatment arm.

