### **3.4                   Study Rationale**

The FDA approved label duration for NS5A-experienced, PI-naïve subjects with or without compensated cirrhosis and HCV GT1 chronic infection is G/P 300 mg/120 mg for 16 weeks. However, the G/P regimen may be further refined based on additional efficacy results in subsets of

NS5A inhibitor experienced, PI-naïve HCV GT1 infected subjects. The goals of this study are to increase the confidence in real world DAA failure patients who are receiving the recommended G/P regimen, to explore a shorter 12-week duration of the G/P regimen in non-cirrhotic subjects, and ribavirin-intensification of a shorter 12-week duration of the G/P regimen in subjects with compensated cirrhosis.

High SVR12 rates were achieved with G/P 300 mg/120 mg when given for 12 and 16 weeks in GT1-infected subjects who were NS5A-experienced and PI-naïve (SVR12 90.0% 18/20 and 94% 17/18, respectively, MAGELLAN-1, NCT02446717, AbbVie, data on file). The majority of subjects with prior NS5A inhibitor-experience in MAGELLAN-1 Part 1 & 2 combined were subjects who failed prior LDV/SOF (Harvoni) treatment: GLE/PIB 300 mg/ 120 mg for 12 weeks (n=12, 11 achieved SVR12, 91.7%), GLE/PIB 300 mg/ 120 mg for 16 weeks (n=10, 9 achieved SVR12, 90.0%), and G/P 300 mg/ 120 mg plus 800 mg once daily RBV for 12 weeks (n=4, all 4 achieved SVR12). Among the 42 NS5A-experienced and PI-naïve failures enrolled in MAGELLAN-1, 30/31 (96.8%) subjects without cirrhosis and 9/11 (81.8%) of subjects with compensated cirrhosis achieved an SVR12.

In MAGELLAN-1, NS5A inhibitor-experienced, PI-naïve subjects without cirrhosis who received G/P 300 mg/120 mg for 12 and 16 weeks achieved SVR12 rates of 92.3% (12/13) and 100% (14/14), respectively. As the difference in SVR12 between these two durations was based on a single subject that did not achieve SVR, it is hypothesized that 12 weeks treatment duration with G/P may provide an effective retreatment option. Therefore, the present study will evaluate G/P for 12 and 16 weeks in a larger patient population to determine if treatment duration may be decreased from 16 to 12 weeks in NS5A inhibitor-experienced, PI-naïve subjects without cirrhosis.

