##### **Randomization scheme:**

-GT1 non-cirrhotic (up to 150) subjects: randomized 2:1 to Arms A or B.

-GT1 cirrhotic (up to 75) subjects: randomized 1:1 to Arm C or D.

[figure not shown]
Randomization will be stratified by HCV GT 1b vs non-1b.

The Main study consists of 2 periods:

**Treatment Period:** Eligible subjects will be enrolled to receive G/P 300 mg/120 mg QD +/- RBV for 12 weeks or G/P for 16 weeks.

**Post Treatment Period:** Subjects who complete or prematurely discontinue the Treatment Period will be followed for 12 weeks after their last dose of study drug to evaluate efficacy and to monitor HCV RNA and the emergence and persistence of viral substitutions.

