### **8.1.2.4 Subgroup Analysis**

In the mITT population for the Main study, association of the proportions of subjects with SVR12 with each of the following subgroups will be compared across treatment arms (Arms A and B, and Arm C and D separately) using Zelen's exact tests. In addition, two-sided 95% Wilson score intervals will be calculated for the difference between Arms A and B and Arms C and D, for the following subgroups:

- HCV GT1 subtype;
- Most recent HCV treatment history;
- All prior HCV treatment history;
- Type of non-response to NS5A-inhibitor+SOF± RBV treatment;
- Sex;
- Age;
- Race;
- Ethnicity;
- BMI;
- Baseline HCV RNA level;

- Baseline platelet count;
- Baseline albumin;
- Baseline APRI;
- Baseline FIB-4;
- Baseline AST/ALT ratio;
- Baseline Child-Pugh Score (for cirrhotic subjects only);
- History of concomitant diseases: (a) diabetes, (b) HIV coinfection (c) post-organ transplant;
- Concomitant use of Proton Pump inhibitors
- DAA compliance.
- Baseline resistance polymorphisms (any NS3/4A variant [yes/no]; any NS5A variant [yes/no]; any NS3/4A and any NS5A [yes/no], any NS3/4A or any NS5A [yes/no]) and [NS3/4A only, NS5A only, both NS3/4A and NS5A, or none]).

The difference in SVR12 rates between G/P given for 12 weeks (Arm A and C combined) and G/P given for 16 weeks (Arm B and D combined) will also be examined within the combined arms by HCV sub-genotype (1b vs. non-1b).

Further details about subgroup analyses will be described in the Statistical Analysis Plan.

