### **8.3 Randomization Methods**

The Main study is randomized. In it, eligible subjects without cirrhosis will be randomized 2:1 into Arms A and B. Subjects with compensated cirrhosis will be randomized 1:1 into Arms C and D. Randomization will be stratified by HCV genotype 1 subtype (1b or non-1b) and cirrhosis status.

The Retreatment sub-study is not randomized; all subjects who experience virologic failure in the Main study and consent to the Retreatment sub-study will receive G/P + SOF  $\pm$  RBV for 16 weeks.

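### The pooled 12-week versus 16-week SVR12 difference is not stratified by cirrhosis, although allocation is 2:1 in non-cirrhotics and 1:1 in cirrhotics, so cirrhosis is confounded with duration by design

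*Protocol*

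**What the plan says.** Protocol Section 8.1.2.2 lists as the first secondary endpoint a comparison, for SVR12, of "rates between G/P given for 12 weeks (Arm A and C combined) and G/P given for 16 weeks (Arm B and D combined". On method it says only that the difference between the two "treatment durations will be summarized calculated along with a two-sided 95% confidence interval using Wilson's score method". It names no weighting or stratification. The synopsis and Section 4.2 carry the same pooled contrast.

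The allocation ratio differs by cirrhosis status. Under the randomization scheme in Section 5.1: "GT1 non-cirrhotic (up to 150) subjects: randomized 2:1 to Arms A or B", and "GT1 cirrhotic (up to 75) subjects: randomized 1:1 to Arm C or D". Section 8.3 repeats the ratios and adds: "Randomization will be stratified by HCV genotype 1 subtype (1b or non-1b) and cirrhosis status".

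The only further breakdown of the pooled difference is in Section 8.1.2.4, which says that it "will also be examined within the combined arms by HCV sub-genotype (1b vs. non-1b"). No breakdown by cirrhosis is planned for it.

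On prognosis, Section 3.4 reports for NS5A-experienced, PI-naive subjects in MAGELLAN-1 that "30/31 (96.8%) subjects without cirrhosis and 9/11 (81.8%) of subjects with compensated cirrhosis achieved an SVR12". Section 3.2 says that failure of ledipasvir/sofosbuvir in the HCV-TARGET cohort was more likely with cirrhosis.

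**The concern.** Randomisation balances Arm A against Arm B, and Arm C against Arm D. It does not balance A+C against B+D, because the probability of receiving 12 weeks is 2/3 without cirrhosis and 1/2 with it. The 16-week pool is bound to contain a larger share of cirrhotic subjects. If cirrhosis lowers SVR12, a crude difference credits the 12-week pool with part of the cirrhosis effect. The discrepancy comes from the allocation ratios and does not shrink as the sample grows.

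The direction matters because the study asks whether treatment can be shortened from the labelled 16 weeks. A bias towards the shorter course would work against a cautious answer. Section 8.2 tabulates deficits of 0 to 2 points for the 12-week arms, so a bias of about 2 points would equal the largest deficit considered there.

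**Working it through.** **Plan's own figures.** The protocol gives no precision or expected value for the pooled contrast. Section 8.2 gives half widths only for A v B (100 and 50 subjects) and C v D (40 and 40). These reproduce with the simple normal formula. For A v B at 92% in both arms, 1.96 × √(0.92 × 0.08/100 + 0.92 × 0.08/50) = 0.092. For C v D at 94% in both arms, 1.96 × √(2 × 0.94 × 0.06/40) = 0.104.

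**Inputs.**
- Non-cirrhotic: up to 150 at 2:1, so A = 100 and B = 50 (Sections 5.1, 8.3).
- Cirrhotic: up to 75 at 1:1, so C = D = 37.5 on average (same sections).
- SVR12 in this population: 30/31 = 96.8% without and 9/11 = 81.8% with cirrhosis (Section 3.4).
- Planning ranges: 92-96% in Arm B (non-cirrhotic) and 94-98% in Arm D (cirrhotic) (Section 8.2).

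**Step 1, composition.** The cirrhotic share is 37.5/137.5 = 27.3% in A+C and 37.5/87.5 = 42.9% in B+D. The difference is 15.6 points.

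**Step 2, bias.** Suppose that neither duration nor ribavirin has an effect, so that SVR12 is pN in all non-cirrhotics and pC in all cirrhotics. Each pooled rate is then a mix of pN and pC, and

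crude difference (12 minus 16 weeks) = (0.429 - 0.273) × (pN - pC) = 0.156 × (pN - pC).

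Each 1-point gap in SVR12 by cirrhosis thus moves the pooled difference by about 0.16 points.

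**Step 3, at the Section 3.4 rates.**
- 12 weeks: (100 × 30/31 + 37.5 × 9/11)/137.5 = 92.7%.
- 16 weeks: (50 × 30/31 + 37.5 × 9/11)/87.5 = 90.4%.
- Crude difference: +2.3 points, where the true difference is 0.

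With 40 per cirrhotic arm, as in Section 8.2, it is +2.4. At the minimum of 175 subjects with 70% non-cirrhotic it is +2.2.

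**Step 4, other gaps.**

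| Source of the gap | pN - pC (points) | Bias (points) |
|---|---|---|
| Section 3.4 rates | 15.0 | +2.3 |
| Assumed | 5 | +0.8 |
| Section 8.2, 96% v 94% | 2 | +0.3 |
| Equal rates | 0 | 0 |
| Section 8.2, 92% v 98% | -6 | -0.9 |

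A bias of 2 points needs a gap of about 0.02/0.156 = 13 points.

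**Step 5, stratified estimate.** The Mantel-Haenszel weights are proportional to 100 × 50/150 = 33.3 and 37.5 × 37.5/75 = 18.75, that is 0.64 and 0.36. At the Section 3.4 rates with no true effect, the weighted difference is 0.0 with a 95% half width of about 7.4 points. If 12 weeks were truly 2 points worse in both strata, the crude difference would be 2.3 - 2.0 = +0.3, while the stratified difference would be -2.0.

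**The case against.** The case on the other side is mostly about size and importance, and much of it stands.

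- **The 15-point gap is weak evidence.** It rests on 11 cirrhotic subjects, and the 95% Newcombe interval for the gap runs from about -3 to +45 points. In the GT1 column of Table 2 (Section 3.1.1), a different and largely easier population, cirrhotics reached 98/101 (97.0%) and the remainder (881 - 98)/(889 - 101) = 783/788 (99.4%). That gap of about 2.3 points implies a bias of only about +0.4. The planning ranges in Section 8.2 allow cirrhotics to do better than non-cirrhotics, which would reverse the sign.
- **Arm C receives ribavirin.** The 9/11 comes from G/P alone (6/7 at 12 weeks and 3/4 at 16 weeks, Section 3.4). Applying 81.8% to Arm C assumes no ribavirin effect.
- **The analysed split may differ.** The mITT population follows the final arm (Section 8.1), and Section 3.4 extends already enrolled PI-exposed subjects from 12 to 16 weeks. The figures of 27.3% and 42.9% describe the planned maximum.
- **The endpoint is secondary and estimation-only.** It has no margin and no decision rule. The primary comparisons, on-treatment failure, relapse and the sensitivity analyses are all done within cirrhosis strata, so a deficit present in both strata would be open to view there. Even +2.3 is less than a third of the 7.4-point half width.
- **Details are left to the SAP.** Section 8.1 defers additional detail, and Section 8.1.2.2 does not use the word unstratified. But it does fix both the contrast and the interval method, and its plain reading is one crude difference.

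None of this removes the imbalance, which follows from the allocation ratios alone.

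**Conclusion.** The point holds, with moderate severity. As written, the pooled difference is confounded by a randomisation stratum. The bias is about 0.16 points per point of SVR12 gap by cirrhosis. With no duration or ribavirin effect and the planned maximum enrolment, this is +2.3 points in favour of 12 weeks at the Section 3.4 rates, +0.8 at an assumed 5-point gap, and about -0.9 to +0.3 across the Section 8.2 ranges.

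The documents do not support three stronger readings that a reader might infer:

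- *12 weeks will look about 2 points better whatever happens.* The imbalance is fixed by design, but its effect on the estimate depends on a gap that the protocol's own figures place anywhere from -6 to +15 points.
- *The primary comparisons share the problem, or need stratifying by 1b v non-1b to escape it.* The allocation ratio is constant within A v B and within C v D, so this mechanism produces no bias there.
- *The sub-genotype breakdown repeats the error.* Section 8.1.2.4 names no method for that breakdown and leaves further detail to the SAP. It needs a matching change for consistency; it is not a second demonstrated fault.

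**What to change.** - In Section 8.1.2.2, the synopsis and the SAP, replace the crude pooled difference with one stratified by cirrhosis status, using Mantel-Haenszel weights and a stratified Newcombe/Wilson interval.
- If the pooled difference is reported by 1b v non-1b (Section 8.1.2.4), use the same cirrhosis-stratified estimator within each sub-genotype.
- State beside the endpoint that, as randomised, ribavirin is given only in Arm C. Stratification removes the confounding by cirrhosis, but the contrast still compares regimens and not duration alone.
- Leave the primary analyses as they are.

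The cost is a few lines of text and standard code, with no new data and no burden on subjects. Weighting by stratum is already familiar in this protocol: the footnotes to Table 2 describe intervals built that way.

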### **4.2 Secondary Objectives**

The secondary objectives are to assess

1. The difference in efficacy (SVR12) of G/P±RBV given for 12 weeks (Arms A+C) versus G/P±RBV given for 16 weeks (Arms B+D).
2. The differences in the percentages of subjects with on-treatment virologic failure for non-cirrhotic subjects (Arm A vs Arm B) and subjects with compensated cirrhosis (Arm C vs Arm D);

3. The differences in the percentages of subjects with post-treatment relapse for non-cirrhotic subjects (Arm A vs Arm B) and subjects with compensated cirrhosis (Arm C vs Arm D).

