### **5.0 Investigational Plan**

#### **5.1 Overall Study Design, Rationale and Plan: Description**

##### **Main Study**

This Phase 3b study has been designed as a multi-center, randomized, open-label, pragmatic study of G/P +/- RBV for 12 weeks or G/P 16 weeks in subjects with chronic HCV GT1 infection who are treatment experienced with NS5A inhibitor + SOF therapy. Up to 225 subjects with chronic GT1 infection and prior treatment history of a NS5A inhibitor +SOF±RBV regimen will be enrolled to receive:

Arm A: G/P (300mg /120mg QD) for 12 weeks

Arm B: G/P (300mg /120mg QD) for 16 weeks

Arm C: G/P (300mg /120mg QD) + wt. based RBV (1000 or 1200mg total daily

dose given BID for patients with body weight <75kg or ≥75kg,  
respectively) for 12 weeks

Arm D: G/P (300mg /120mg QD) for 16 weeks

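### The pooled 12- versus 16-week SVR12 difference is not stratified by cirrhosis, although 2:1 and 1:1 allocation put cirrhotics at 27.3% of one pool and 42.9% of the other

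*Protocol*

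**What the plan says.** Section 8.1.2.2 (and the synopsis) takes SVR12 as the outcome of its first secondary endpoint and compares "rates between G/P given for 12 weeks (Arm A and C combined) and G/P given for 16 weeks (Arm B and D combined". Results for the two "treatment durations will be summarized calculated along with a two-sided 95% confidence interval using Wilson's score method". No stratum, weight or covariate is mentioned.

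The randomization scheme in section 5.1 uses different ratios by cirrhosis status: non-cirrhotic "subjects: randomized 2:1 to Arms A or B" (up to 150), cirrhotic "subjects: randomized 1:1 to Arm C or D" (up to 75). Section 8.3 adds: "Randomization will be stratified by HCV genotype 1 subtype (1b or non-1b) and cirrhosis status".

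The sensitivity analyses in section 8.1.2.3 cover A vs B and C vs D only. The one further look at the pooled contrast, in section 8.1.2.4, "will also be examined within the combined arms by HCV sub-genotype (1b vs. non-1b", so it uses the same pools.

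The pools are also labelled inconsistently. Section 4.2 speaks of 12 weeks "versus G/P±RBV given for 16 weeks (Arms B+D", which attaches ribavirin to both pools; section 8.1.2.2 attaches it to neither; section 5.1 describes a "study of G/P +/- RBV for 12 weeks or G/P 16 weeks in subjects with chronic HCV GT1 infection". The arms are always named, so the label alone changes no result.

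**The concern.** When allocation ratios differ between strata, merging the strata gives two groups with different case mix. This follows from the design and is not a chance imbalance, so neither randomization nor a larger sample removes it. If SVR12 differs by cirrhosis status, the merged difference is non-zero even when the regimens perform identically within each stratum.

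The protocol treats cirrhosis as prognostic. The introduction lists it as a host factor in treatment failure, section 3.2 reports more failures with cirrhosis in an observational cohort, and section 8.3 stratifies on it. If cirrhotics respond less well, the error flatters the 12-week regimens, which section 3.4 calls experimental, against the approved 16-week duration.

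**Working it through.** **Plan's own figures.** The protocol gives no precision figure for the pooled contrast. Section 8.2 gives half-widths for A vs B (100/50) and C vs D (40/40). These reproduce with the simple normal formula: at 92% in both arms, 1.96 × √(0.92 × 0.08 × (1/100 + 1/50)) = 0.092, as printed. This confirms the arm sizes used below.

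**Pool composition.** With 150 non-cirrhotics at 2:1, A = 100 and B = 50. With 75 cirrhotics at 1:1, C = D = 37.5 on average.
- Cirrhotic share at 12 weeks: 37.5/137.5 = 27.3%.
- Cirrhotic share at 16 weeks: 37.5/87.5 = 42.9%.
- Gap: 15.6 points. With the 40/40 of section 8.2 it is 44.4% - 28.6% = 15.9. With the minimum of 175 subjects split 117/58 (assumed), it is 42.6% - 27.1% = 15.5.

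**Shift with no treatment effect.** Let pN and pC be SVR12 in non-cirrhotics and cirrhotics, the same for both durations. Then

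12-week pool minus 16-week pool = (share at 16 weeks - share at 12 weeks) × (pN - pC) = 0.1558 × (pN - pC).

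| Source of rates | pN | pC | Shift (points) |
|---|---|---|---|
| Section 3.4: 30/31 and 9/11 | 96.8% | 81.8% | +2.3 |
| Section 8.2, midpoints | 94% | 96% | -0.3 |
| Section 8.2, one extreme | 92% | 98% | -0.9 |
| Section 8.2, other extreme | 96% | 94% | +0.3 |

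In the first row the pooled rates are 92.7% and 90.4%. A true loss of 2 points with 12 weeks in both strata would then appear as 2.33 - 2 = +0.33 points.

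**Interval width.** I read Wilson's score method for a difference as the Newcombe interval, which is an assumption. The stratified version combines the stratum Newcombe limits with Mantel-Haenszel weights: 100 × 50/150 = 33.33 and 37.5 × 37.5/75 = 18.75, that is 0.64 and 0.36.
- Section 3.4 rates: crude interval -4.9 to +11.0 (half-width 7.9 points); stratified half-width 8.1.
- 94%/96%: crude interval -6.3 to +7.0 (half-width 6.6); stratified half-width 7.3.

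**Simulation with no effect** (400,000 trials, arms 100/50/38/37):

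| Rates | Method | Covers zero | Wholly above zero (nominal 2.5%) |
|---|---|---|---|
| 96.8% / 81.8% | Crude | 90.6% | 9.0% |
| 96.8% / 81.8% | Stratified | 96.5% | 2.3% |
| 94% / 96% | Crude | about 95% | about 2.4% |
| 94% / 96% | Stratified | 97.4% | about 1.8% |

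**Subtype breakdown.** Randomization is also stratified by subtype, so both ratios apply within 1b and within non-1b. The imbalance recurs in each. Its size depends on the cirrhotic proportion within the subtype, which the protocol does not give.

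**The case against.** - **The text does not say unstratified.** A stratified Newcombe interval is still a Wilson-score method, and further detail is deferred to the SAP. However, the protocol fixes the arms as combined and gives one difference with one interval. Reading that as already stratified is strained.
- **The harm rests on 11 cirrhotics.** This stands as a limit on size. The Newcombe 95% interval for the gap between 30/31 and 9/11 runs from about -3 to +45 points. In the larger GT1 data of Table 2 (an easier population: treatment-naïve, or experienced without an NS5A or protease inhibitor), cirrhotics reached 98/101 (97.0%) and the rest 783/788 (99.4%). That gap of 2.3 points shifts the contrast by under 0.4. Over the section 8.2 ranges the shift is small and crude coverage is about nominal. The mechanism is not in doubt; its size and sign are.
- **The shares are not fixed.** They assume full caps, while analysis is by final treatment arm. If 10% of A and of C were reclassified to 16 weeks (assumed), the shares would be 33.75/123.75 = 27.3% and 41.25/101.25 = 40.7%, a gap of about 13.5 points. The imbalance remains.
- **Stratifying does not isolate duration.** C vs D also differs by ribavirin, so the weighted average still mixes two contrasts. This stands, and should be stated in the plan. Stratifying removes the case-mix error only.
- **No decision depends on it.** The endpoint is secondary and estimation-only, and per-arm rates are reported. This limits the priority, but not the case for correcting it.

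**Conclusion.** The point holds. As written, the pooled secondary contrast partly measures case mix, carrying about 15.6% of whatever SVR12 gap separates non-cirrhotics from cirrhotics. That is +2.3 points at the section 3.4 rates and -0.9 to +0.3 over the section 8.2 ranges, against a crude half-width of 6.6 to 7.9 points. The documents do not settle the sign. These figures assume the planned caps are filled and the Newcombe reading of the interval. The consequence is confined to one estimation-only secondary endpoint and its subtype breakdown; A vs B and C vs D are not touched. The change should be made, but the primary results do not depend on it.

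**What to change.** In section 8.1.2.2 and the synopsis, define the 12-week minus 16-week SVR12 difference as stratified by cirrhosis status, for example with Mantel-Haenszel weights and a stratified Wilson/Newcombe interval. Keep the mITT population by final treatment arm. Use the same estimator for the 1b/non-1b breakdown in section 8.1.2.4. State that the contrast compares regimens (C includes ribavirin) and that conclusions on G/P duration rest on A vs B.

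While editing, the pool labels in the synopsis and in sections 4.2, 8.1.2.2 and 8.1.2.4 could follow the section 5.1 description, with any ribavirin added under section 5.4.1.1 reported separately. This is tidying and does not affect the main point.

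No new data are needed, since cirrhosis status is already a randomization stratum. The cost is a slightly more complex and somewhat wider interval: half-width 8.1 against 7.9 points at the section 3.4 rates, and 7.3 against 6.6 at 94%/96%, where it is also mildly conservative.
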